1.6 Exploratory Analysis

- 1.6.1 We will quantify any differential treatment response by heart failure subtype (HFPEF, HFrEF) by including heart failure subtype as a covariate and as an interaction with the group effects in the models mentioned above.

1.7 Sample Size Determination

- 1.7.1 Sample size was determined based on a combination of feasibility and also the variability of 24-h net urine output observed in the ATHENA-HF trial (Butler et al. 2017). Butler et al. observed a median (25th percentile, 75th percentile) net urine output of 1183 ml (510, 1955) in the usual care alone group and 1100 ml (483, 2131) in the high dose spironolactone group. **With a total sample size of 20 patients (10 per group), we will have 80% power at the alpha=0.05 level of significance (two-sided) to detect a 1688 ml difference in 24-h urine output assuming a common standard deviation of 1200 ml and a dropout rate of 10% or less.** With all other assumptions being the same, the following gives estimates of power for a range of differences. Power was estimated using nQuery Advisor version 7.0 (two group t-test of equal means).

Difference (mL)	Power
1500	70%
1600	75%
1700	80%
1800	84%
1900	88%
2000	91%

1.8 Randomization

1.8.1 Participants will be randomized in a 1:1 fashion while maintaining a level of unpredictability to future randomization assignment. The randomization sequences will be prepared by the study statistician ([name]) using random variable block sizes of two or four patients per block. REDCap's randomization module will be used to reveal the randomized assignment on a per-patient basis by pharmacy staff.

1.9 Blinding

1.9.1 Patients and all study staff will be blind to the randomization assignment except for pharmacy staff and the study statistician.

1.10 Multiplicity Considerations

1.10.1 We will report unadjusted p-values and describe the correlation of primary and secondary outcomes in publications to allow for additional researchers to evaluate the robustness of the findings.

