Study Product, Dose, Route, Regimen	Patients will be randomized 1:1 to ultra-high dose (IV bumetanide 12.5 mg bid) vs standard dose (IV furosemide as twice the home dose of oral daily diuretic in furosemide equivalents administered bid) for 24 hours. Participants will undergo comprehensive physiological assessment at baseline and 24 hours with short Iohexol clearance for true glomerular filtration rate, apnea hypopnea index, electrocardiography, echocardiography, serum, and urine biomarkers. Patients will be monitored for side effects including muscle cramps, new onset atrial fibrillation (AF), sustained ventricular tachycardia (VT), symptomatic hypotension (MAP<60 or systolic blood pressure <80 mmHg), development of renal insufficiency and dialysis initiation.
Duration of Administration	Patients will be on therapy for 24 hours.

Statistical Methodology	The primary efficacy endpoint is urine output over 24 hours which will be compared by T test between the two groups. Primary safety endpoint will be incident decline in creatinine estimated glomerular filtration rate by 50% over 24 hours. Key secondary endpoints include weight change, NT-proBNP change, urine output, urine sodium excretion, creatinine, and cystatin C estimated GFR changes, apnea-hypopnea index, Iohexol glomerular filtration rate, serum and urine proteomic analyses, peripheral vein pressure and echocardiographic changes over 24 hours, estimated GFR at day 7 or discharge (whichever is sooner) will each be compared by T test between the two groups.
-------------------------	---

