3.3 Exploratory Objectives

- a) To compare length of hospital stay in the ultrahigh versus usual dose groups
- b) To compare total diuretic use in hospital between the ultrahigh versus usual dose groups
- c) To compare 90-day heart failure rehospitalizations between the ultrahigh versus usual dose groups
- d) To compare creatinine based GFR changes from baseline to day 7 or discharge (whichever is sooner) between ultrahigh versus usual dose groups
- e) To explore proteomic changes in blood and urine between the ultrahigh versus usual dose groups
- f) To examine changes in apnea-hypopnea index between ultrahigh and usual dose groups
- g) To determine daytime and nighttime blood pressure patterns between ultrahigh and usual dose groups
- h) To compare arterial stiffness alterations between ultrahigh and usual dose groups
- i) To explore changes in liver elastography in the ultrahigh versus usual dose groups

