In this pilot study we will therefore compare an ultra-high diuretic strategy with a conventional diuretic strategy in patients with decompensated heart failure with a primary efficacy end point of urine output at 24 hours. The primary safety endpoint will be a decline in serum creatinine estimated GFR by 50% of baseline value at 24 hours. This will be a double-blinded randomized pilot trial of ultra-high dose diuretics (IV bumetanide 12.5 mg bid for 24 hours vs IV furosemide at usual doses (twice the home dose of oral daily diuretic in furosemide equivalents administered bid). New initiation of adjunct diuretics (thiazide, SGLT2 inhibitors, acetazolamide, and spironolactone) will be discouraged during the 24-hour study period. Key secondary endpoints include weight change, NT-proBNP change, urine output, urine sodium excretion, creatinine, and cystatin C estimated GFR changes, apnea-hypopnea index, iohexol glomerular filtration rate, serum and urine proteomic analyses, peripheral vein pressure and echocardiographic changes over 24 hours, estimated GFR at day 7 or discharge (whichever is sooner) will each be compared by T test between the two groups.

4.2 Hypothesis:

Ultrahigh dose diuretic infusion will be associated with greater diuretic response and will not be associated with clinically significant decline in eGFR over 24 hours (defined as decline in creatinine estimated GFR of 50% from baseline at 24 hours).

4.3 Innovation:

1. Ultra-high dose diuretic strategies have not been compared to conventional diuretic strategies in a randomized trial
2. The use of a double-blind strategy will minimize bias in terms of diuretic adjustment and alternative therapies.
3. The measurement of serum and urine biomarkers of renal injury, peripheral vein pressure and echocardiography changes at baseline and at 24 hours will provide novel insight into the hemodynamic, renal, and cardiac response to decongestion.

4. The relationship between creatinine based GFR during non-steady state conditions such as active diuresis and extracellular volume reduction during diuresis, and true GFR measured by lohexol clearance testing has never been studied.
5. The effect of rapid diuresis on cardiac structure and function has not been well studied
6. The short-term effect of rapid volume removal on measures of sleep is unknown

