7. Proteomic changes associated with high versus usual dose diuretics will be assessed to evaluate for differential expression of key pathways between the two strategies

4.4 .Significance:

1. The demonstration of safety and efficacy with ultra-high dose diuretic strategy compared to conventional diuretic infusion will be an important safety and preliminary efficacy finding to support a multicenter randomized phase III trial for superiority in relation to clinical outcomes.
2. Delineating mechanisms of hemodynamic benefit to more aggressive decongestion and relationship to renal indices will advance our understanding of human cardiorenal syndrome

4.5 Brief Synopsis of Methods:

- Accrual of 20 patients with decompensated heart failure requiring hospitalization randomized to ultra-high vs conventional dose diuretic arms in a double-blind design over 24 hours. Anticipate 25 patients will be enrolled to accrue 20 patients.
- Baseline assessment of renal lohexol clearance, echocardiography, blood sampling and urine sampling and nocturnal Watch Pat one assessment (apnea-hypopnea index), with all above assessments repeated after 24 hours.
- Follow up phone assessment at 90 days to assess heart failure readmission rates.

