1.4 Primary Analysis

- 1.4.1 The primary analysis will be to compare urine output at 24 hours after initiation of intravenous diuretic. All patients meeting eligibility criteria who provide informed consent, are randomized, and receive any dose of intravenous diuretic will be included in the primary analysis based on intention-to-treat (ITT) principles. The difference in 24-hour urine output between groups will be estimated using a linear regression model; 95% confidence intervals will be constructed using t-based methods. A p-value less than 0.050 will be considered statistically significant.

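### Proteomics is to be compared by t test with unadjusted p-values and no false discovery control, so any list of differing proteins would carry no stated error rate

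*Combined protocol and SAP*

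**What the plan says.** - **Status as key secondary.** The Statistical Methodology row of the Study Summary includes "serum and urine proteomic analyses, peripheral vein pressure and echocardiographic changes over 24 hours" in its list of key secondary endpoints. Section 4.1 repeats the list and says that its members "will each be compared by T test between the two groups".
- **Status as exploratory.** Section 3.3(e) gives the same analysis as an exploratory objective: "To explore proteomic changes in blood and urine between the ultrahigh versus usual dose groups".
- **Purpose.** Section 4.3, item 7: "Proteomic changes associated with high versus usual dose diuretics will be assessed to evaluate for differential expression of key pathways".
- **Multiplicity.** SAP 1.10 is the only rule: "We will report unadjusted p-values". It adds that publications will describe how the primary and secondary outcomes correlate, and it makes no exception for proteomics.
- **Threshold.** SAP 1.4, on the primary analysis: "A p-value less than 0.050 will be considered statistically significant". No threshold is stated for proteins.
- **What is absent.** Proteomics is in neither the outcome list of 11.4.2.1 nor that of SAP 1.3.2. The documents give no platform, number of proteins, criterion for calling a protein different, or false discovery method.

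**The concern.** Unadjusted p-values are tolerable for a short list of clinical outcomes that a reader can count and weigh. They are harder to defend for proteomics, where each of two fluids may yield many tests and the result is normally read as a list of proteins that differ. Without an error rate attached to that list, a reader cannot tell how much of it is chance.

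The stated aim goes beyond single proteins to pathways, so unreliable protein-level calls could carry through to the mechanistic conclusions. The trial is meant to inform a later, larger trial, and a chance-driven pathway finding could misdirect that work.

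**Working it through.** **1. The plan's own figure.** SAP 1.7 states 80% power for a 1688 mL difference with SD 1200 mL, two-sided alpha 0.05, 10 per group and dropout of 10% or less. With 9 evaluable per group (10 × 0.9), the exact two-sample t-test calculation (noncentral t, 16 degrees of freedom) gives 79.99%. The plan's table for 1500 to 2000 mL (70, 75, 80, 84, 88, 91%) recomputes as 70.2, 75.7, 80.5, 84.8, 88.3 and 91.3%. The sample-size figure is sound, and 9 per arm is used below. The documents state no false-positive figure for proteomics.

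**2. False flags among unaffected proteins.** The expected number is 0.05 × the number of unaffected proteins. This assumes that the 0.05 level is applied to each protein. Panel size is also an assumption.
- 100 unaffected proteins: 0.05 × 100 = 5 per fluid.
- 1000 unaffected proteins: 0.05 × 1000 = 50 per fluid.
- Chance of at least one false flag among 100 independent unaffected proteins: 1 − 0.95^100 = 99.4%.

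**3. False share of the flagged proteins.** Let π be the share of proteins that truly differ and P the power per protein. Then

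false share = 0.05(1 − π) / [0.05(1 − π) + Pπ].

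Neither π nor the effect sizes are in the documents, so a range is shown. With 9 per arm, P is 0.358, 0.800 and 0.978 for standardized effects d of 0.8, 1.41 and 2.0. The middle value is the plan's own urine-output effect, 1688/1200 = 1.41.

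| π | d = 0.8 | d = 1.41 | d = 2.0 |
|---|---|---|---|
| 1% | 93% | 86% | 84% |
| 5% | 73% | 54% | 49% |
| 10% | 56% | 36% | 32% |
| 20% | 36% | 20% | 17% |

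Worked examples:
- π = 5%, d = 0.8: 0.0475 / (0.0475 + 0.0179) = 73%.
- π = 20%, d = 2.0: 0.0400 / (0.0400 + 0.1956) = 17%.

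**4. When more than half are false.** Setting the false share to 50% gives π = 0.05 / (0.05 + P). The break-even is about 12% at d = 0.8 (0.05/0.408), 6% at d = 1.41 (0.05/0.850) and 5% at d = 2.0 (0.05/1.028). Below these shares most flagged proteins are false; above them most are true.

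**5. Effect of false discovery control.** This was simulated with 1000 independent proteins (assumed), 5% truly different and 9 per arm.

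| d | Flagged, unadjusted p < 0.05 | False share | Flagged, Benjamini-Hochberg 5% |
|---|---|---|---|
| 0.8 | 65 | 72% | 0.2 |
| 1.41 | 87 | 54% | 7 |
| 2.0 | 96 | 49% | 36 |

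The average false proportion under Benjamini-Hochberg was about 3 to 5% in these three settings. The unadjusted column agrees with the formula in step 3.

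**The case against.** **Tempting stronger readings.** A reader might infer that most proteins called different will be false. The documents do not support that. It depends on the share of proteins affected and the size of the effects, neither of which is given, and step 3 shows results from 17% to 93%. Counting false flags when no protein differs cannot settle the matter, because every flag is then false by definition. A reader might also infer that the plan rejects false discovery control. It does not: SAP 1.10 speaks of primary and secondary outcomes, the SAP's own list leaves proteomics out, and reporting unadjusted p-values does not exclude reporting q-values as well. The plan is silent.

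**The case for leaving the plan alone.** This is a 20-patient pilot sized on feasibility and urine output. Proteomics is already an exploratory objective, and no primary claim or stopping rule depends on it. The 0.050 threshold is stated only for the primary analysis, and nothing says that pathway results will be built from proteins below it. Strict control at this sample size may also leave almost nothing to follow up.

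**What stands.** The limits on the inference stand and are carried into the verdict. They do not supply an error rate, however. Two places call proteomics key secondary, and the only multiplicity rule has no exception. If SAP 1.10 is read as not reaching proteomics, then no multiplicity rule covers it, and the same addition is needed. The loss of discoveries is a real cost, but showing q-values beside nominal p-values keeps the ranking available for generating hypotheses.

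**Conclusion.** The point holds in a limited form. As written, the plan gives t-test comparisons for proteomics with unadjusted p-values, no false discovery control and an inconsistent status (key secondary in two places, exploratory in a third, absent from the SAP outcome list).

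If 0.05 is used for each protein, about 5% of unaffected proteins will be flagged in each fluid. The false share of the flagged list would be roughly half to three quarters if 5% of proteins truly differ, and about a sixth to a third if 20% do. A majority of false calls is therefore conditional on sparse or modest effects. These figures rest on 9 evaluable patients per arm, standardized effects of 0.8 to 2.0, and assumed shares of truly different proteins. The primary analysis and its power calculation are unaffected.

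**What to change.** Add to SAP 1.10 that, for serum and urine proteomics:
- Benjamini-Hochberg q-values across all proteins measured within each fluid will be reported beside nominal p-values, at a false discovery rate fixed in advance (for example 5% or 10%);
- any claim of differential expression or pathway enrichment will rest on the q-values;
- the analysis is exploratory, as in 3.3(e), and the number of proteins tested in each fluid will be stated.

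Bring the Study Summary and section 4.1 into line with that status. Unadjusted p-values can stay for the clinical secondary outcomes listed in SAP 1.3.2.

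The cost is a short addition to the SAP, two wording changes and a line of code, with no extra data. The downside is that few or no proteins may be declared different at this sample size; nominal p-values remain for ranking candidates.

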12. DATA COLLECTION AND QUALITY ASSURANCE

12.1 Data Collection Forms

The study case report form (CRF) is the primary data collection instrument for the study. All data requested on the CRF must be recorded. All missing data must be explained. If a space on the CRF is left blank because the procedure was not done or the question was not asked, write "N/D". If the item is not applicable to the individual case, write "N/A". All entries should be printed legibly in black ink. If any entry error has been made, to correct such an error, draw a single straight line through the incorrect entry and enter the correct data above it. All such changes must be initialed and dated. Do not erase or use "white-out" for errors. For clarification of illegible or uncertain entries, print the clarification above the item, then initial and date it. If the reason for the correction is not clear or needs additional explanation, neatly include the details to justify the correction.

The data collection tool for this study will be sponsor defined case report forms. The investigator will maintain complete and accurate study documentation in a separate file. Study documentation may include medical records, records detailing the progress of the study for each subject, signed informed consent forms, drug disposition records, correspondence with the study coordinator/study monitor/sponsor, screening and consent information, severe adverse event reports, laboratory reports, subject diaries, data clarifications requested by the sponsor, and any other documentation deemed relevant and pertinent to the study and the study subjects. Subject data necessary for analysis and reporting will be entered into a validated database or data system in accordance. Clinical data management will be performed in accordance with applicable data management vendor standards and data cleaning procedures. The investigator is responsible for the procurement of data and for the quality of data recorded on the CRFs. The handling of data, including data quality assurance, will comply with regulatory guidelines.

Source data is all information, original records of clinical findings, observations, or other activities in a clinical trial necessary for the reconstruction and evaluation of the trial. Source data are contained in source documents. Examples of these original documents, and data records include: hospital records, clinical and office charts, laboratory notes, records kept at the pharmacy, at the laboratories, and at medico-technical departments involved in the clinical trial.

The investigator will maintain records and essential documents related to the conduct of the study. These will include subject case histories and regulatory documents.

12.2 Data Management

All study data will be collected at Mayo Clinic with the Department of Cardiovascular Diseases as the primary coordinating and data management center.

REDCap will be used for clinical data management and randomization. These tools are institutionally supported and allow for rapid database development. The implementation of the software within a project includes training on the system's use, robust error checking, security considerations, and full audit trail. Balance, which is integrated into *REDCap*, allows for a variety of randomization and minimization algorithms.

Demographic and clinical data will be extracted from medical records including age and gender, vital signs, physical exam findings.

For biospecimens, NT-pro-BNP, creatinine, hematocrit and cystatin C, urine sodium will be measured in real time, and the remainder will be stored for future analysis of cardiac biomarkers.

The echocardiographic parameters that will be captured comprise: systolic, diastolic LV and RV function parameters including LVEF by M-Mode, 2 D, biplane Simpson, lateral and medial E/e', left atrial volume index, right ventricular size and function, tissue velocities of the tricuspid annulus, TAPSE, lung ultrasound for B lines, IVC diameter/collapse, internal jugular dimension/size relative to carotid.

All individually identifiable patient records and data will be stored in a database under coded accession numbers. A password is required to gain access to this protected and privileged information. Only the approved and trained study staff will have access to the database. For individuals providing data, e.g., core laboratory personnel, access will be limited to entering data only. All data are monitored regularly for entry and access, and a formal policy regarding protection of personal privacy is in place throughout Mayo Foundation. The key to identification of subjects will be maintained in a secure office environment under the direction of the investigators. The institutional commitment at Mayo Clinic to protect patients' (and study participants') privacy is a high priority.

12.3 Quality Assurance

12.3.1 Training

The study will be performed only by adequately trained personnel. This applies to the entire study team roster. Only approved and trained study staff, experienced in trials such as these, will interact with the patients and manage the data forms and database. The echocardiography and laboratory teams are likewise experienced in these types of trials as is the section of biostatistics at Mayo.

12.3.2 Quality Control Committee

This study will not assemble a quality control committee.

12.3.3 Metrics

The primary outcome measure is urine volume. We will compare change in urine volume to body weight change as a metric of accurate urine output collection. Source document verification will be performed to ensure data fidelity as well. To ensure compliance with applicable regulatory requirements, the sponsor or designee may conduct a quality assurance audit. Regulatory agencies may also conduct a regulatory inspection of this study. Such audits/inspections can occur at any time during or after completion of the study. If an audit or inspection occurs, the investigator and institution agree to allow the auditor/inspector direct access to all relevant documents and to allocate his/her time and the time of his/her staff to the auditor/inspector to discuss findings and any relevant issues.

12.3.4 Protocol Deviations

Protocol deviations in diuretic administration and/or adjunct diuretic use will be recorded

12.3.5 Monitoring

The investigator will permit study-related monitoring, audits, and inspections by the IRB, the sponsor of all study related documents (e.g., source documents, regulatory documents, data collection instruments, study data etc.). The investigator will ensure the capability for inspections of applicable study-related facilities (e.g., pharmacy, diagnostic laboratory, etc.).

Participation as an investigator in this study implies acceptance of potential inspection by government regulatory authorities and applicable compliance offices.

13. PARTICIPANT RIGHTS AND CONFIDENTIALITY

The study will employ standard methods for protecting the confidentiality of research materials through the use of coded identification numbers that are specific to the study on all materials except those that are necessary for participant contact, follow-up, and ongoing linkage with data such as those from medical records, using password-protected computer data files and databases, and locked file cabinets for storing hard copies of any other study materials. Only study personnel who need to track participants for follow-up purposes have access to the identifying information for individual study participants. No personally identifiable information (protected health information) except the minimum necessary for study purposes are shared with co-investigators, and any sharing of data is by encrypted, password-protected data files. In addition to the procedures outlined above, confidentiality and privacy are further enhanced as each institution maintains research databases behind institution-specific password-protected firewalls.

Blood specimens will be stored in appropriate freezers coded with study-specific identification numbers and barcodes with no other identifying information on them. Barcodes include information on time of storage and are linked to a password-protected research laboratory information management system (RLIMS) database that was built specifically for these purposes. Study staff members are trained to follow established confidentiality procedures. Samples will be kept in central, secured repository. Should it become necessary to ship samples to collaborating investigators for approved sub-analyses, this will be done without any identifying information except for study-specific identification numbers.

Echocardiographic images will be stored on a secured data platform.

No preliminary or final results will be released or published with identifying information or reported on an individual level, and all epidemiologic data will be presented as statistical summaries. No statistics will be published based on fewer than 5 subjects, a practice consistent with HIPAA and most confidentiality guidelines.

A description of the plan for data and safety monitoring and adverse event reporting to the IRB, the Data and Safety Monitoring Board, the NIH and others, as appropriate, is provided in the Data and Safety Monitoring Plan to ensure the safety of subjects.

Information about study subjects will be kept confidential and managed according to the requirements of the Health Insurance Portability and Accountability Act of 1996 (HIPAA). Those regulations require a signed subject authorization informing the subject of the following:

- What protected health information (PHI) will be collected from subjects in this study
- Who will have access to that information and why?
- Who will use or disclose that information?
- The rights of a research subject to revoke their authorization for use of their PHI.

In the event that a subject revokes authorization to collect or use PHI, the investigator, by regulation, retains the ability to use all information collected prior to the revocation of subject authorization. For subjects that have revoked authorization to collect or use PHI, attempts should

be made to obtain permission to collect at least vital status (long term survival status that the subject is alive) at the end of their scheduled study period.

